APPENDIX 4. VISIT-WINDOW MAPPING

Document:	[REDACTED]	Version Number:	2.5
Author:	[REDACTED]	Version Date:	18Feb2022
Template No.:	[REDACTED]	Reference:	CS_WI_BS005

Effective Date: 02Dec2019

	Cycle 1				Cycle 2-3		Cycle 4 and onwards	Post-treatment
Visit	C1D1	C1D8	C1D15	C1D22	CxD1	CxD15	CxD1	
Scheduled Day [a]	1	8	15	22	1	15	1	
ECOG	Day 1		2 to EOC-3		Day -3 to 3	4 to EOC-3	Day -3 to 3	Last dose date of last cycle +8 to last dose date +37
Vital Sign	Day 1	2 to 11	12 to 18	19 to EOC-3	Day -3 to 3	4 to EOC-3	Day -3 to 3	
Hematology		1 to 11	12 to 18	19 to EOC-3	Day -3 to 3	4 to EOC-3	Day -3 to 3	
Coagulation		1 to 11	12 to 18	19 to EOC-3	Day -3 to 3	4 to EOC-3	Day -3 to 3	
Clinical Chemistry		1 to 11	12 to 18	19 to EOC-3	Day -3 to 3	4 to EOC-3	Day -3 to 3	
Urinalysis		1 to 11	12 to 18	19 to EOC-3	Day -3 to 3	4 to EOC-3	Day -3 to 3	
Thyroid function		1 to 11	12 to 18	19 to EOC-3	Day -3 to 3	4 to EOC-3	Day -3 to 3	
12-Led ECG	Day 1		2 to EOC-3		Day -3 to 3		Day -3 to 3	

[a] The scheduled day is relative to the Day 1 of each cycle.

Note: The end date of a cycle (EOC) is defined as the one day earlier than the date of Day 1 study drug administration of its next cycle. For the last cycle (where no subsequent cycle is given), the end of cycle will be defined as Day 7 relative to the last dose of the cycle.

Tumor Assessment

	Cycle 2	Cycle 3	Cycle 4	8 Weeks after D1 of Cycle 4	8 * (X + 1) Weeks after D1 of Cycle 4 [b]	Post-treatment
Visit	C2D1	C3D1	C4D1	8 Weeks after D1 of Cycle 4	8 * (X + 1) Weeks after D1 of Cycle 4 [b]	
Scheduled Day [a]	1	1	1	57	1 + 7*8 * (X + 1)	
Tumor Assessment (Cohort A and B)	-3 to (EOC-3)	-3 to (EOC-3)	-3 to (EOC-3)	End of Cycle 4 to 85	28 * (2X + 1) + 2 to 28 * (2X + 3) + 1 [d]	Last dose date of last cycle +8 to last dose date +37
	Week 8	Week 8 * (X + 1)				
Visit	Week 8	Week 8 * (X + 1) [b]				
Scheduled Day [c]	57	1 + 7*8 * (X + 1)				
Tumor Assessment (Cohort C, D, and E)	Day 2 to 85	28 * (2X + 1) + 2 to 28 * (2X + 3) + 1 [d]				

[a] The scheduled day is relative to the Day 1 for Cycle 2 to Cycle 4, but the subsequent scheduled day is relative to Day 1 of Cycle 4.

[b] X is an intergerrn starting from 1, and will take maximum value at date of last study drug administration.

[c] Scheduled day is relative to Day 1 of Cycle 1.

[d] The last windowed visit end by the last dose date.

Note: The end date of a cycle (EOC) is defined as the one day earlier than the date of Day 1 study drug administration of its next cycle. For the last cycle (where no subsequent cycle is given), the end of cycle will be defined as Day 7 relative to the last dose of the cycle.

Document: [REDACTED]

Author: [REDACTED]

Version Number:

2.5

Version Date:

18Feb2022

Template No.: [REDACTED]

Reference: CS_WI_BS005

Effective Date: 02Dec2019

Echocardiogram

		Week 12 * (X + 1)	Post-treatment
Visit	Week 12	Week 12 * (X + 1) [b]	
Scheduled Day [c]	85	$1 + 7 * 12 * (X + 1)$	
Echocardiogram	Day 2 to 127	$42 * (2X + 1) + 2$ to $42 * (2X + 3) + 1$ [c]	Last dose date of last cycle +8 to last dose date +37

[a] The scheduled day is relative to the Day 1 of Cycle 1.

[b] X is an intergern starting from 1, and will take maximum value at date of last study drug administration.

[c] The last windowed visit end by the last dose date.

Document:

[REDACTED]

Author:

[REDACTED]

Version Number:

2.5

Version Date:

18Feb2022

Template No.:

[REDACTED]

Reference: CS_WI_BS005

Effective Date: 02Dec2019

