5.2. BASELINE

Unless otherwise specified, baseline is defined as the last non-missing measurement taken prior to reference start date (including unscheduled assessments). In the case where the last non-missing measurement and the reference start date coincide, that measurement will be considered baseline, unless additional information collected on eCRF indicate otherwise.

For example, ECG will be considered being performed post-baseline if assessment date coincides with the reference start date but “Time Point” on “ECG (ECG)” form indicates the assessment was performed “Post-dose 3 hours (\pm 15 minutes)”. Adverse Events (AEs) onset on the reference start date and with “Did the adverse event occur prior to the start of study treatment?” in “Adverse Events (AE)” form answered as “No” or not being answered will be considered as post-baseline. Medications commencing the reference start date will be considered post-baseline.

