5.3. UNSCHEDULED VISITS AND EARLY TERMINATION DATA

In general, for by-visit summaries, data recorded at the nominal visit will be presented. Unscheduled measurements will not be included in by-visit summaries, but will contribute to the best/ worst case value where required (e.g., shift table).

Listings will include scheduled, unscheduled, and early discontinuation data.

Document: [REDACTED]

Author: [REDACTED]

Version Number:

2.5

Version Date:

18Feb2022

Template No.: [REDACTED]

Reference: CS_WI_BS005

Effective Date: 02Dec2019

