5.4. WINDOWING CONVENTIONS

The visit-window mapping is described in [APPENDIX 4](#). Visit-based summaries will be based on the windowed visits. All data, whether or not within the visit windows, will be presented in listings.

For windowed visits during the treatment cycles,

- If more than 1 assessment occurs during a visit window, the assessment closest to the scheduled day will be assigned to the windowed visit.
- If two assessments are equidistant from the scheduled day, the later assessment will be assigned to the windowed visit.
- If there are multiple assessments on the same day, the worst case will be used.

For the post-treatment visit, the last assessment in the window will be included in the summary. The window for the post-treatment visit will be "from the last dose date + 8 days to the last dose date + 37 days".

For a patient who prematurely discontinues the study, the premature visit will be slotted accordingly.

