17.8.2. ECHOCARDIOGRAM

Baseline and change from baseline on left ventricular ejection fraction (LVEF) will be summarized by dose cohort (only in dose escalation phase) or tumor specific cohorts (only in dose expansion phase) and visit. Also, shift from baseline to worst post-baseline overall evaluation (i.e., normal, abnormal but NCS, abnormal and CS) will be summarized. Individual data will also be listed.

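### SAP Appendix 4 leaves the seven days after the last dose outside every visit, so an on-schedule echocardiogram at Week 24 or later is lost from by-visit LVEF when the patient does not start the next cycle

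*SAP*

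**What the plan says.** SAP Appendix 4 maps each assessment to a visit. For echocardiograms the first window (Week 12) is Day 2 to 127. The repeating windows are 42(2X+1)+2 to 42(2X+3)+1 for X = 1, 2, and so on, and they carry note [c]: "The last windowed visit end by the last dose date". The repeating scan windows carry the same sentence as note [d]. The notes are not printed on the Week-12 echo window or on the Week-8 scan window of Cohorts C to E (Day 2 to 85).

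The post-treatment window in Appendix 4 is "Last dose date of last cycle +8 to last dose date +37", and SAP 5.4 agrees: "from the last dose date + 8 days to the last dose date + 37 days". Section 5.4 adds "For the post-treatment visit, the last assessment in the window will be included in the summary", and also "Visit-based summaries will be based on the windowed visits".

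SAP 17.8.2 supplies the output at issue: "Baseline and change from baseline on left ventricular ejection fraction (LVEF) will be summarized by dose cohort", and by visit. Its other LVEF table is a shift from baseline to the worst post-baseline overall rating (normal, abnormal not clinically significant, abnormal clinically significant).

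Two neighbouring rules also matter. On by-visit summaries, SAP 5.3 says "data recorded at the nominal visit will be presented" and leaves out unscheduled measurements. On Day 1 values, SAP 5.2 says "In the case where the last non-missing measurement and the reference start date coincide, that measurement will be considered baseline".

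**The concern.** A mapping rule should place an assessment by when it was due, not by whether the patient went on to another cycle. Here the due date for the next echo can fall just after the last dose, at the point where continuing or stopping is decided. The same echo on the same day counts towards Week 24 if the patient starts Cycle 7, and does not if the patient stops.

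Decreased LVEF is an adverse event category of special interest in SAP 17.2.6, and SAP 17.8.2 has no numeric worst-value summary that would pick up a displaced echo. The post-treatment row is not a dependable substitute, because a later echo in that window replaces an earlier one.

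**Working it through.** **Inputs.** Dosing on Days 1 to 21 of a 28-day cycle (SAP 15). Echo every 12 weeks ±1 week, plus one at treatment completion, 30 ±7 days after permanent discontinuation (protocol Appendix A). Window formulas, notes [c] and [d] and the post-treatment window from SAP Appendix 4.

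**Reproducing the plan's figures.** Setting X = 0 in the window-end formulas gives 42 × 3 + 1 = 127 for echo and 28 × 3 + 1 = 85 for scans, both as printed.

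**Last dose and due date.** The last dose of cycle c is on Day 28(c − 1) + 21. For c = 6 this is Day 161. The Week-24 echo is scheduled on Day 1 + 84 × 2 = 169, which is last dose +8. The protocol interval is Day 162 to 176 (15 days).

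**Mapping for a patient who does not start Cycle 7.** The printed Week-24 window is Day 128 to 211. Note [c] cuts it to Day 128 to 161. Post-treatment runs from 161 + 8 = 169 to 161 + 37 = 198.

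| Days | Visit | Count |
|---|---|---|
| 162–168 | none | 7 |
| 169–176 | post-treatment | 8 |
| any | Week 24 | 0 |

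Later echo visits split the same way (Day 253 after a last dose on Day 245; Day 337 after Day 329). So do the repeating scan windows of Cohorts C to E: Week 16 is due on Day 113, and after a last dose on Day 105, Days 106–112 are unmapped and Days 113–120 are post-treatment.

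**Stopping earlier in the cycle.** If the last dose is on day k of the cycle, the next Day 1 is 29 − k days later: +15 for k = 14, +22 for k = 7, +28 for k = 1. Even with the ±7 days these lie between +8 and +35, so they are all post-treatment and none reaches the scheduled visit.

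**Replacement within post-treatment.** Suppose the echo is done and the decision to stop is taken on Day 169. The completion visit is then due on Day 192 to 206 (169 + 23 to 169 + 37). A completion echo by Day 198 replaces the Day-169 value.

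**First windows.** With no note attached, a Week-12 echo after a last dose on Day 77 stays in Week 12 on all 15 days (78 to 92). Days 85 to 92 also lie in post-treatment, which opens on 77 + 8 = 85. The Week-8 scan behaves alike: after a last dose on Day 49, Days 57 to 64 lie in both. No precedence rule is given.

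**Cycle 1 Day 8 laboratory window.** It runs from Day 1 to Day 11, whereas the vital-sign window starts on Day 2. Under the closest-to-scheduled rule, Day 1 is 7 days from Day 8, and every day from 2 to 11 is nearer. A Day 1 value that SAP 5.2 makes baseline therefore enters as Cycle 1 Day 8, with change 0, only when nothing else falls in Days 2 to 11.

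**SAP 5.3 against 5.4.** Section 5.3 uses the value recorded at the nominal visit and excludes unscheduled values. Section 5.4 uses the assessment in the window that lies closest to the scheduled day. The two can give different tables from the same data.

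**The case against.** The strongest reply is that little depends on these windows. SAP 16.2 summarizes only the best percentage change in tumor size, with a waterfall plot. BOR and PFS are dated by scans, and the rule for two missed assessments is a fixed 126 days. The LVEF shift table uses the worst post-baseline rating, and AESI incidence, severity and time to onset come from adverse event records. Individual LVEF values are listed. All of this stands.

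The first affected echo is also late. The protocol cites a median PFS of 3.71 months in the phase 3 colorectal trial, about 3.71 × 30.4375 = 113 days, so many colorectal patients may have stopped before Day 169. That also stands, though PFS is not time on treatment.

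An off-drug echo labelled post-treatment can be defended as a convention. That covers days +8 onward but not the unmapped week. SAP 5.4 does say that a premature visit will be assigned suitably, but not to which visit.

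A reader might infer that by-visit LVEF and tumor size describe only patients who continued. The documents do not support this. No by-visit tumor size summary is described, echoes on or before the last dose still count for patients who then stop, and the first windows are not cut. A reader might also see a contradiction with the Appendix 4 note that ends the last cycle 7 days after its last dose. The windows carrying [c] and [d] are not defined through the end of cycle, so this is a gap rather than a conflict.

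On the smaller points, the laboratory issue needs a Day 1 sample. The protocol's schedule as read shows none, while the copy in the SAP appears to. On 5.3, its opening qualifier suggests that 5.4 is meant to govern, but eligibility of unscheduled values stays open.

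**Conclusion.** The concern holds in a narrow form. As written, notes [c] and [d] leave last dose +1 to +7 in no visit for the repeating windows. An on-schedule echo at Week 24 or later, in a patient who does not start the next cycle, never reaches its scheduled visit: 7 of the 15 protocol days are lost to any visit row and 8 go to post-treatment. The by-visit LVEF change summary is affected from Week 24 onward; the primary endpoint is not.

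The day counts assume dosing to Day 21 with no cycle delays. They are shares of calendar days, not of patients, and the documents give no basis for the number of patients affected. It is tempting to add that LVEF decline is understated. Nothing in the documents shows that patients who stop have lower LVEF, so the direction of any bias is open. The laboratory window and the disagreement between 5.3 and 5.4 are real but minor.

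**What to change.** 1. In Appendix 4, change notes [c] and [d] so that the last window runs to last dose +7 days. Alone this recovers Days 162–168 in the example but still misses the due date, Day 169, at +8.
2. Add that an assessment within ±7 days of its scheduled day stays with that scheduled visit and takes precedence over the post-treatment window, for the first windows as well. This recovers the other 8 days and settles the overlaps at Week 8 and Week 12.
3. Start the Cycle 1 Day 8 laboratory windows on Day 2, as for vital signs.
4. State that SAP 5.4 governs by-visit summaries, and whether unscheduled values are eligible.

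The cost is SAP wording and window programming. No further data are needed, since the assessments and their dates are already collected.

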APPENDIX 5. MEDDRA (VERSION 24.1) PREFERRED TERM LIST FOR AESI CATEGORIES

AESI Category: Thyroid Dysfunction		
Anti-thyroid antibody	Marine Lenhart syndrome	Thyroid size decreased
Anti-thyroid antibody decreased	Multifocal fibrosclerosis	Thyroid stimulating hormone deficiency
Anti-thyroid antibody increased	Myxoedema	Thyroid stimulating immunoglobulin increased
Anti-thyroid antibody positive	Myxoedema coma	Thyroid therapy
Antithyroid arthritis syndrome	Orbital decompression	Thyroid tuberculosis
Atrophic thyroiditis	Photon radiation therapy to thyroid	Thyroidectomy
Autoimmune hypothyroidism	Polyglandular autoimmune syndrome type II	Thyroiditis
Autoimmune thyroid disorder	Polyglandular autoimmune syndrome type III	Thyroiditis acute
Autoimmune thyroiditis	Post procedural hypothyroidism	Thyroiditis chronic
Basedow's disease	Primary hyperthyroidism	Thyroiditis fibrous chronic
Biopsy thyroid gland abnormal	Primary hypothyroidism	Thyroiditis subacute
Blood thyroid stimulating hormone abnormal	Protein bound iodine decreased	Thyrotoxic cardiomyopathy
Blood thyroid stimulating hormone decreased	Protein bound iodine increased	Thyrotoxic crisis
Blood thyroid stimulating hormone increased	Radioactive iodine therapy	Thyrotoxic myopathy
Butanol-extractable iodine decreased	Radiotherapy to thyroid	Thyrotoxic periodic paralysis
Butanol-extractable iodine increased	Reverse tri-iodothyronine decreased	Thyroxine binding globulin abnormal
Congenital hypothyroidism	Reverse tri-iodothyronine increased	Thyroxine binding globulin decreased
Congenital thyroid disorder	Secondary hyperthyroidism	Thyroxine binding globulin increased
Endocrine ophthalmopathy	Secondary hypothyroidism	Thyroxine abnormal
Euthyroid sick syndrome	Silent thyroiditis	Thyroxine decreased
Exophthalmos	Tertiary hypothyroidism	Thyroxine free abnormal
Free thyroxine index abnormal	Thyreostatic therapy	Thyroxine free decreased
Free thyroxine index decreased	Thyroglobulin absent	Thyroxine free increased
Free thyroxine index increased	Thyroglobulin decreased	Thyroxine increased
Gamma radiation therapy to thyroid	Thyroglobulin increased	Thyroxine therapy

Document: [REDACTED]

Author: [REDACTED]

Version Number:

2.5

Version Date:

18Feb2022

Template No.: [REDACTED]

Reference: CS_WI_BS005

Effective Date: 02Dec2019

Generalised resistance to thyroid hormone	Thyroglobulin present	Toxic goitre
Goitre	Thyroid atrophy	Toxic nodular goitre
Hashimoto's encephalopathy	Thyroid autotransplantation	Transient hypothyroxinaemia of prematurity
Hashitoxicosis	Thyroid dermatopathy	Tri-iodothyronine abnormal
Hyperthyroidism	Thyroid disorder	Tri-iodothyronine decreased
Hypothyroidic goitre	Thyroid dysfunction in pregnancy	Tri-iodothyronine free abnormal
Hypothyroidism	Thyroid electron radiation therapy	Tri-iodothyronine free decreased
Immune-mediated hyperthyroidism	Thyroid function test abnormal	Tri-iodothyronine free increased
Immune-mediated hypothyroidism	Thyroid gland scan abnormal	Tri-iodothyronine free normal
Immune-mediated thyroiditis	Thyroid hemiagenesis	Tri-iodothyronine increased
Inappropriate thyroid stimulating hormone secretion	Thyroid hormone replacement therapy	Tri-iodothyronine uptake abnormal
Infectious thyroiditis	Thyroid hormones decreased	Tri-iodothyronine uptake decreased
Iodine uptake abnormal	Thyroid hormones increased	Tri-iodothyronine uptake increased
Iodine uptake decreased	Thyroid operation	Ultrasound thyroid abnormal
Iodine uptake increased	Thyroid pain	X-ray therapy to thyroid
Malignant exophthalmos	Thyroid releasing hormone challenge test abnormal	
AESI Category: Proteinuria		
Albumin globulin ratio increased	Beta 2 microglobulin urine increased	Protein urine
Albumin urine present	Globulinuria	Protein urine present
Albuminuria	Microalbuminuria	Proteinuria
Bence Jones protein urine present	Myoglobinuria	Urine albumin/creatinine ratio increased
Bence Jones proteinuria	Orthostatic proteinuria	Urine protein/creatinine ratio abnormal
		Urine protein/creatinine ratio increased
AESI Category: Hypertension		
Accelerated hypertension	Eclampsia	Metabolic syndrome
Aldosterone urine abnormal	Ectopic aldosterone secretion	Metanephrine urine abnormal
Aldosterone urine increased	Ectopic renin secretion	Metanephrine urine increased

Document: [REDACTED]

Author: [REDACTED]

Version Number: 2.5

Version Date: 18Feb2022

Template No.: [REDACTED]

Reference: CS_WI_BS005

Effective Date: 02Dec2019

Angiotensin converting enzyme increased	Endocrine hypertension	Neurogenic hypertension
Angiotensin I increased	Epinephrine abnormal	Non-dipping
Angiotensin II increased	Epinephrine increased	Norepinephrine abnormal
Angiotensin II receptor type 1 antibody positive	Essential hypertension	Norepinephrine increased
Blood aldosterone abnormal	Gestational hypertension	Normetanephrine urine increased
Blood aldosterone increased	HELLP syndrome	Orthostatic hypertension
Blood catecholamines abnormal	Hyperaldosteronism	Page kidney
Blood catecholamines increased	Hypertension	Postoperative hypertension
Blood pressure abnormal	Hypertension neonatal	Pre-eclampsia
Blood pressure ambulatory abnormal	Hypertensive angiopathy	Prehypertension
Blood pressure ambulatory increased	Hypertensive cardiomegaly	Procedural hypertension
Blood pressure diastolic abnormal	Hypertensive cardiomyopathy	Pseudoaldosteronism
Blood pressure diastolic increased	Hypertensive cerebrovascular disease	Renal hypertension
Blood pressure fluctuation	Hypertensive crisis	Renal sympathetic nerve ablation
Blood pressure inadequately controlled	Hypertensive emergency	Renal vascular resistance increased
Blood pressure increased	Hypertensive encephalopathy	Renin abnormal
Blood pressure management	Hypertensive end-organ damage	Renin increased
Blood pressure orthostatic abnormal	Hypertensive heart disease	Renin-angiotensin system inhibition
Blood pressure orthostatic increased	Hypertensive nephropathy	Renovascular hypertension
Blood pressure systolic abnormal	Hypertensive urgency	Retinopathy hypertensive
Blood pressure systolic increased	Labile blood pressure	Secondary aldosteronism
Catecholamine crisis	Labile hypertension	Secondary hypertension
Catecholamines urine abnormal	Malignant hypertension	Superimposed pre-eclampsia
Catecholamines urine increased	Malignant hypertensive heart disease	Supine hypertension
Dialysis induced hypertension	Malignant renal hypertension	Systolic hypertension
Diastolic hypertension	Maternal hypertension affecting foetus	Tyramine reaction
Diuretic therapy	Mean arterial pressure increased	Withdrawal hypertension
AESI Category: Haemorrhages		

Document: [REDACTED]

Author: [REDACTED]

Version Number: 2.5

Version Date: 18Feb2022

Template No.: [REDACTED]

Reference: CS_WI_BS005

Effective Date: 02Dec2019

Abdominal wall haematoma	Haemophilic pseudotumour	Petechiae
Abdominal wall haemorrhage	Haemoptysis	Pharyngeal contusion
Abnormal uterine bleeding	Haemorrhage	Pharyngeal haematoma
Abnormal withdrawal bleeding	Haemorrhage coronary artery	Pharyngeal haemorrhage
Achenbach syndrome	Haemorrhage foetal	Pituitary apoplexy
Acute haemorrhagic leukoencephalitis	Haemorrhage in pregnancy	Pituitary haemorrhage
Acute haemorrhagic ulcerative colitis	Haemorrhage intracranial	Placenta praevia haemorrhage
Administration site bruise	Haemorrhage neonatal	Polymenorrhagia
Administration site haematoma	Haemorrhage subcutaneous	Post abortion haemorrhage
Administration site haemorrhage	Haemorrhage subepidermal	Post procedural contusion
Adrenal haematoma	Haemorrhage urinary tract	Post procedural haematoma
Adrenal haemorrhage	Haemorrhagic adrenal infarction	Post procedural haematuria
Anal fissure haemorrhage	Haemorrhagic arteriovenous malformation	Post procedural haemorrhage
Anal haemorrhage	Haemorrhagic ascites	Post transfusion purpura
Anal ulcer haemorrhage	Haemorrhagic breast cyst	Postmenopausal haemorrhage
Anastomotic haemorrhage	Haemorrhagic cerebellar infarction	Postpartum haemorrhage
Anastomotic ulcer haemorrhage	Haemorrhagic cerebral infarction	Post-traumatic punctate intraepidermal haemorrhage
Aneurysm ruptured	Haemorrhagic cyst	Premature separation of placenta
Angina bullosa haemorrhagica	Haemorrhagic diathesis	Procedural haemorrhage
Anorectal varices haemorrhage	Haemorrhagic disease of newborn	Proctitis haemorrhagic
Anticoagulant-related nephropathy	Haemorrhagic disorder	Prostatic haemorrhage
Antiplatelet reversal therapy	Haemorrhagic erosive gastritis	Pulmonary alveolar haemorrhage
Aortic aneurysm rupture	Haemorrhagic gastroenteritis	Pulmonary contusion
Aortic dissection rupture	Haemorrhagic hepatic cyst	Pulmonary haematoma
Aortic intramural haematoma	Haemorrhagic infarction	Pulmonary haemorrhage
Aortic perforation	Haemorrhagic necrotic pancreatitis	Pulmonary haemorrhage neonatal
Aortic rupture	Haemorrhagic occlusive retinal vasculitis	Puncture site bruise
Aponeurosis contusion	Haemorrhagic ovarian cyst	Puncture site haematoma
Application site bruise	Haemorrhagic stroke	Puncture site haemorrhage

Document: [REDACTED]

Author: [REDACTED]

Version Number: 2.5

Version Date: 18Feb2022

Template No.: [REDACTED]

Reference: CS_WI_BS005

Effective Date: 02Dec2019

Application site haematoma	Haemorrhagic thyroid cyst	Purpura
Application site haemorrhage	Haemorrhagic transformation stroke	Purpura fulminans
Application site purpura	Haemorrhagic tumour necrosis	Purpura neonatal
Arterial haemorrhage	Haemorrhagic urticaria	Purpura non-thrombocytopenic
Arterial intramural haematoma	Haemorrhagic vasculitis	Purpura senile
Arterial perforation	Haemorrhoidal haemorrhage	Putamen haemorrhage
Arterial rupture	Haemostasis	Radiation associated haemorrhage
Arteriovenous fistula site haematoma	Haemothorax	Rectal haemorrhage
Arteriovenous fistula site haemorrhage	Heavy menstrual bleeding	Rectal ulcer haemorrhage
Arteriovenous graft site haematoma	Henoch-Schonlein purpura	Renal artery perforation
Arteriovenous graft site haemorrhage	Hepatic haemangioma rupture	Renal cyst haemorrhage
Astringent therapy	Hepatic haematoma	Renal haematoma
Atrial rupture	Hepatic haemorrhage	Renal haemorrhage
Auricular haematoma	Hereditary haemorrhagic telangiectasia	Respiratory tract haemorrhage
Basal ganglia haematoma	Hyperfibrinolysis	Respiratory tract haemorrhage neonatal
Basal ganglia haemorrhage	Hypergammaglobulinaemic purpura of Waldenstrom	Retinal aneurysm rupture
Basilar artery perforation	Hyphaema	Retinal haemorrhage
Bladder tamponade	Iliac artery perforation	Retinopathy haemorrhagic
Bleeding varicose vein	Iliac artery rupture	Retroperitoneal haematoma
Blood blister	Iliac vein perforation	Retroperitoneal haemorrhage
Blood loss anaemia	Immune thrombocytopenia	Retroplacental haematoma
Blood urine	Implant site bruising	Ruptured cerebral aneurysm
Blood urine present	Implant site haematoma	Scleral haematoma
Bloody discharge	Implant site haemorrhage	Scleral haemorrhage
Bloody peritoneal effluent	Incision site haematoma	Scrotal haematocoele
Bone contusion	Incision site haemorrhage	Scrotal haematoma
Bone marrow haemorrhage	Increased tendency to bruise	Scrotal haemorrhage
Brain contusion	Induced abortion haemorrhage	Shock haemorrhagic
Brain stem haematoma	Inferior vena cava perforation	Skin haemorrhage

Document: [REDACTED]

Author: [REDACTED]

Version Number: 2.5

Version Date: 18Feb2022

Template No.: [REDACTED]

Reference: CS_WI_BS005

Effective Date: 02Dec2019

Brain stem haemorrhage	Infusion site bruising	Skin neoplasm bleeding
Brain stem microhaemorrhage	Infusion site haematoma	Skin ulcer haemorrhage
Breast haematoma	Infusion site haemorrhage	Small intestinal haemorrhage
Breast haemorrhage	Injection site bruising	Small intestinal ulcer haemorrhage
Broad ligament haematoma	Injection site haematoma	Soft tissue haemorrhage
Bronchial haemorrhage	Injection site haemorrhage	Spermatic cord haemorrhage
Bronchial varices haemorrhage	Instillation site bruise	Spinal cord haematoma
Bullous haemorrhagic dermatosis	Instillation site haematoma	Spinal cord haemorrhage
Bursal haematoma	Instillation site haemorrhage	Spinal epidural haematoma
Cardiac contusion	Intermenstrual bleeding	Spinal epidural haemorrhage
Carotid aneurysm rupture	Internal haemorrhage	Spinal subarachnoid haemorrhage
Carotid artery perforation	Intestinal haematoma	Spinal subdural haematoma
Catheter site bruise	Intestinal haemorrhage	Spinal subdural haemorrhage
Catheter site haematoma	Intestinal varices haemorrhage	Spleen contusion
Catheter site haemorrhage	Intra-abdominal haematoma	Splenic artery perforation
Central nervous system haemorrhage	Intra-abdominal haemorrhage	Splenic haematoma
Cephalhaematoma	Intracerebral haematoma evacuation	Splenic haemorrhage
Cerebellar haematoma	Intracranial haematoma	Splenic varices haemorrhage
Cerebellar haemorrhage	Intracranial tumour haemorrhage	Splinter haemorrhages
Cerebellar microhaemorrhage	Intraocular haematoma	Spontaneous haematoma
Cerebral aneurysm perforation	Intrapartum haemorrhage	Spontaneous haemorrhage
Cerebral aneurysm ruptured syphilitic	Intratumoural haematoma	Stoma site haemorrhage
Cerebral arteriovenous malformation haemorrhagic	Intraventricular haemorrhage	Stomatitis haemorrhagic
Cerebral artery perforation	Intraventricular haemorrhage neonatal	Subarachnoid haematoma
Cerebral cyst haemorrhage	Iris haemorrhage	Subarachnoid haemorrhage
Cerebral haematoma	Joint microhaemorrhage	Subarachnoid haemorrhage neonatal
Cerebral haemorrhage	Jugular vein haemorrhage	Subcapsular hepatic haematoma
Cerebral haemorrhage foetal	Kidney contusion	Subcapsular renal haematoma
Cerebral haemorrhage neonatal	Lacrimal haemorrhage	Subcapsular splenic haematoma

Document: [REDACTED]

Author: [REDACTED]

Version Number:

2.5

Version Date:

18Feb2022

Template No.: [REDACTED]

Reference: CS_WI_BS005

Effective Date: 02Dec2019

Cerebral microhaemorrhage	Large intestinal haemorrhage	Subchorionic haematoma
Cervix haematoma uterine	Large intestinal ulcer haemorrhage	Subchorionic haemorrhage
Cervix haemorrhage uterine	Laryngeal haematoma	Subclavian artery perforation
Chest wall haematoma	Laryngeal haemorrhage	Subclavian vein perforation
Choroidal haematoma	Lip haematoma	Subcutaneous haematoma
Choroidal haemorrhage	Lip haemorrhage	Subdural haematoma
Chronic gastrointestinal bleeding	Liver contusion	Subdural haematoma evacuation
Chronic pigmented purpura	Lower gastrointestinal haemorrhage	Subdural haemorrhage
Ciliary body haemorrhage	Lower limb artery perforation	Subdural haemorrhage neonatal
Coital bleeding	Lymph node haemorrhage	Subendocardial haemorrhage
Colonic haematoma	Mallory-Weiss syndrome	Subgaleal haematoma
Conjunctival haemorrhage	Mediastinal haematoma	Subgaleal haemorrhage
Contusion	Mediastinal haemorrhage	Subretinal haematoma
Corneal bleeding	Medical device site bruise	Superior vena cava perforation
Cullen's sign	Medical device site haematoma	Testicular haemorrhage
Cystitis haemorrhagic	Medical device site haemorrhage	Thalamus haemorrhage
Deep dissecting haematoma	Melaena	Third stage postpartum haemorrhage
Diarrhoea haemorrhagic	Melaena neonatal	Thoracic haemorrhage
Disseminated intravascular coagulation	Meningorrhagia	Thrombocytopenic purpura
Diverticulitis intestinal haemorrhagic	Menometrorrhagia	Thrombotic thrombocytopenic purpura
Diverticulum intestinal haemorrhagic	Mesenteric haematoma	Thyroid haemorrhage
Duodenal ulcer haemorrhage	Mesenteric haemorrhage	Tongue haematoma
Duodenitis haemorrhagic	Mouth haemorrhage	Tongue haemorrhage
Ear haemorrhage	Mucocutaneous haemorrhage	Tonsillar haemorrhage
Ecchymosis	Mucosal haemorrhage	Tooth pulp haemorrhage
Encephalitis haemorrhagic	Muscle contusion	Tooth socket haemorrhage
Enterocolitis haemorrhagic	Muscle haemorrhage	Tracheal haemorrhage
Epidural haemorrhage	Myocardial haemorrhage	Traumatic haematoma
Epistaxis	Myocardial rupture	Traumatic haemorrhage

Document: [REDACTED]

Author: [REDACTED]

Version Number: 2.5

Version Date: 18Feb2022

Template No.: [REDACTED]

Reference: CS_WI_BS005

Effective Date: 02Dec2019

Exsanguination	Naevus haemorrhage	Traumatic haemothorax
Extra-axial haemorrhage	Nail bed bleeding	Traumatic intracranial haematoma
Extradural haematoma	Nasal septum haematoma	Traumatic intracranial haemorrhage
Extradural haematoma evacuation	Neonatal gastrointestinal haemorrhage	Tumour haemorrhage
Extravasation blood	Nephritis haemorrhagic	Ulcer haemorrhage
Eye contusion	Nipple exudate bloody	Umbilical cord haemorrhage
Eye haematoma	Occult blood positive	Umbilical haematoma
Eye haemorrhage	Ocular retrobulbar haemorrhage	Umbilical haemorrhage
Eyelid bleeding	Oesophageal haemorrhage	Upper gastrointestinal haemorrhage
Eyelid contusion	Oesophageal intramural haematoma	Ureteric haemorrhage
Eyelid haematoma	Oesophageal ulcer haemorrhage	Urethral haemorrhage
Femoral artery perforation	Oesophageal varices haemorrhage	Urinary bladder haematoma
Femoral vein perforation	Oesophagitis haemorrhagic	Urinary bladder haemorrhage
Foetal-maternal haemorrhage	Omental haemorrhage	Urinary occult blood
Fothergill sign positive	Optic disc haemorrhage	Urinary occult blood positive
Gallbladder haematoma	Optic nerve sheath haemorrhage	Urogenital haemorrhage
Gastric haemorrhage	Oral blood blister	Uterine haematoma
Gastric occult blood positive	Oral contusion	Uterine haemorrhage
Gastric ulcer haemorrhage	Oral mucosa haematoma	Vaccination site bruising
Gastric ulcer haemorrhage, obstructive	Oral purpura	Vaccination site haematoma
Gastric varices haemorrhage	Orbital haematoma	Vaccination site haemorrhage
Gastritis alcoholic haemorrhagic	Orbital haemorrhage	Vaginal haematoma
Gastritis haemorrhagic	Osteorrhagia	Vaginal haemorrhage
Gastroduodenal haemorrhage	Ovarian haematoma	Varicose vein ruptured
Gastrointestinal anastomotic haemorrhage	Ovarian haemorrhage	Vascular access site bruising
Gastrointestinal haemorrhage	Palpable purpura	Vascular access site haematoma
Gastrointestinal polyp haemorrhage	Pancreatic haemorrhage	Vascular access site haemorrhage
Gastrointestinal ulcer haemorrhage	Pancreatic pseudocyst haemorrhage	Vascular access site rupture
Gastrointestinal vascular malformation haemorrhagic	Pancreatitis haemorrhagic	Vascular anastomotic haemorrhage

Document: [REDACTED]

Author: [REDACTED]

Version Number:

2.5

Version Date:

18Feb2022

Template No.: [REDACTED]

Reference: CS_WI_BS005

Effective Date: 02Dec2019

Genital contusion	Papillary muscle haemorrhage	Vascular graft haemorrhage
Genital haemorrhage	Paranasal sinus haematoma	Vascular pseudoaneurysm ruptured
Gingival bleeding	Paranasal sinus haemorrhage	Vascular purpura
Graft haemorrhage	Parathyroid haemorrhage	Vascular rupture
Grey Turner's sign	Parotid gland haemorrhage	Vein rupture
Haemangioma rupture	Pelvic haematoma	Venous haemorrhage
Haemarthrosis	Pelvic haematoma obstetric	Venous perforation
Haematemesis	Pelvic haemorrhage	Ventricle rupture
Haematochezia	Penile contusion	Vertebral artery perforation
Haematocoele	Penile haematoma	Vessel puncture site bruise
Haematoma	Penile haemorrhage	Vessel puncture site haematoma
Haematoma evacuation	Peptic ulcer haemorrhage	Vessel puncture site haemorrhage
Haematoma infection	Pericardial haemorrhage	Vitreous haematoma
Haematoma muscle	Perineal haematoma	Vitreous haemorrhage
Haematosalpinx	Periorbital haematoma	Vulval haematoma
Haematospermia	Periorbital haemorrhage	Vulval haematoma evacuation
Haematotympanum	Periosteal haematoma	Vulval haemorrhage
Haematuria	Peripartum haemorrhage	Withdrawal bleed
Haematuria traumatic	Peripheral artery aneurysm rupture	Wound haematoma
Haemobilia	Peripheral artery haematoma	Wound haemorrhage
Haemoperitoneum	Peripheral exudative haemorrhagic chorioretinopathy	
Haemophilic arthropathy	Peritoneal haematoma	
	Periventricular haemorrhage neonatal	
AESI Category: Gastrointestinal perforation		
Abdominal abscess	Focal peritonitis	Oesophageal perforation
Abdominal hernia perforation	Gastric fistula	Oesophageal rupture
Abdominal wall abscess	Gastric fistula repair	Oesophageal ulcer perforation
Abscess intestinal	Gastric perforation	Oesophageal-pulmonary fistula

Document: [REDACTED]

Author: [REDACTED]

Version Number: 2.5

Version Date: 18Feb2022

Template No.: [REDACTED]

Reference: CS_WI_BS005

Effective Date: 02Dec2019

Acquired tracheo-oesophageal fistula	Gastric ulcer perforation	Oesophagobronchial fistula
Anal abscess	Gastric ulcer perforation, obstructive	Oesophagomediastinal fistula
Anal fistula	Gastrointestinal anastomotic leak	Oesophagopleural fistula
Anal fistula infection	Gastrointestinal fistula	Pancreatic fistula
Anal fistula repair	Gastrointestinal fistula repair	Pancreatic fistula repair
Anastomotic ulcer perforation	Gastrointestinal perforation	Peptic ulcer perforation
Anovulvar fistula	Gastrointestinal ulcer perforation	Peptic ulcer perforation, obstructive
Aortoenteric fistula	Gastropneural fistula	Peptic ulcer repair
Aorto-oesophageal fistula	Gastrosplenic fistula	Perforated ulcer
Appendiceal abscess	Ileal perforation	Perineal abscess
Appendicitis perforated	Ileal ulcer perforation	Perirectal abscess
Arterioenteric fistula	Incisional hernia perforation	Peritoneal abscess
Atrio-oesophageal fistula	Inguinal hernia perforation	Peritoneocutaneous fistula
Chemical peritonitis	Intestinal fistula	Peritonitis
Colon fistula repair	Intestinal fistula infection	Peritonitis bacterial
Colonic abscess	Intestinal fistula repair	Pneumoperitoneum
Colonic fistula	Intestinal perforation	Pneumoretroperitoneum
Colo-urethral fistula	Intestinal ulcer perforation	Procedural intestinal perforation
Diverticular fistula	Jejunal perforation	Rectal abscess
Diverticular perforation	Jejunal ulcer perforation	Rectal fistula repair
Diverticulitis intestinal perforated	Large intestinal ulcer perforation	Rectal perforation
Douglas' abscess	Large intestine perforation	Rectoprostatic fistula
Duodenal perforation	Lower gastrointestinal perforation	Rectourethral fistula
Duodenal rupture	Mesenteric abscess	Retroperitoneal abscess
Duodenal ulcer perforation	Neonatal intestinal perforation	Small intestinal perforation
Duodenal ulcer perforation, obstructive	Oesophageal abscess	Small intestinal ulcer perforation
Duodenal ulcer repair	Oesophageal fistula	Spontaneous bacterial peritonitis
Enterocolonic fistula	Oesophageal fistula repair	Umbilical hernia perforation
Enterocutaneous fistula		Upper gastrointestinal perforation

Document: [REDACTED]

Author: [REDACTED]

Version Number: 2.5

Version Date: 18Feb2022

Template No.: [REDACTED]

Reference: CS_WI_BS005

Effective Date: 02Dec2019

Fistula of small intestine		
AESI Category: Embolic and thrombotic events		
Acute aortic syndrome	Embolism venous	Pseudo-occlusion of internal carotid artery
Acute myocardial infarction	Endarterectomy	Pulmonary artery occlusion
Administration site thrombosis	Eye infarction	Pulmonary artery therapeutic procedure
Adrenal thrombosis	Femoral artery embolism	Pulmonary artery thrombosis
Amaurosis	Fluorescence angiogram abnormal	Pulmonary embolism
Amaurosis fugax	Foetal cerebrovascular disorder	Pulmonary endarterectomy
Angiogram abnormal	Foetal vascular malperfusion	Pulmonary infarction
Angiogram cerebral abnormal	Gastric infarction	Pulmonary microemboli
Angiogram peripheral abnormal	Graft thrombosis	Pulmonary thrombosis
Angioplasty	Haemorrhagic adrenal infarction	Pulmonary tumour thrombotic microangiopathy
Antiphospholipid syndrome	Haemorrhagic cerebral infarction	Pulmonary vein occlusion
Aortic bypass	Haemorrhagic infarction	Pulmonary veno-occlusive disease
Aortic embolus	Haemorrhagic stroke	Pulmonary venous thrombosis
Aortic surgery	Haemorrhagic transformation stroke	Quadriplegia
Aortic thrombosis	Haemorrhoids thrombosed	Quadriplegia
Aortogram abnormal	Hemiparesis	Renal artery angioplasty
Application site thrombosis	Hemiplegia	Renal artery occlusion
Arterectomy	Heparin-induced thrombocytopenia	Renal artery thrombosis
Arterectomy with graft replacement	Hepatic artery embolism	Renal embolism
Arterial angioplasty	Hepatic artery occlusion	Renal infarct
Arterial bypass operation	Hepatic artery thrombosis	Renal vascular thrombosis
Arterial graft	Hepatic infarction	Renal vein embolism
Arterial occlusive disease	Hepatic vascular thrombosis	Renal vein occlusion
Arterial revascularisation	Hepatic vein embolism	Renal vein thrombosis
Arterial stent insertion	Hepatic vein occlusion	Renal-limited thrombotic microangiopathy
Arterial therapeutic procedure	Hepatic vein thrombosis	Retinal artery embolism

Document: [REDACTED]

Author: [REDACTED]

Version Number: 2.5

Version Date: 18Feb2022

Template No.: [REDACTED]

Reference: CS_WI_BS005

Effective Date: 02Dec2019

Arterial thrombosis	Homans' sign positive	Retinal artery occlusion
Arteriogram abnormal	Hypothenar hammer syndrome	Retinal artery thrombosis
Arteriogram carotid abnormal	Iliac artery embolism	Retinal infarction
